# 6.2 Study Agent Accountability Procedures

CBD will be stored by the study personnel securely under the PI's individual schedule 1 DEA registration and New York Bureau of Narcotics Enforcement (BNE) class 7 license in accordance with all applicable laws and

#### #S17-00949

regulations. Additionally, a NYS BNE class 9 importer license and a DEA importer permit will be obtained by the schedule I license and registration holder prior to importation of study drug and study initiation. CBD will be stored in a double-locked refrigerator. The refrigerator is located in a designated research room, with limited access to the PI and study staff only, within the NYU-HHC CTSI Facility, which is located at [name]. The Primary Investigator will oversee the appropriate storage, accountability and dispensing of the study medication and all study drug administration to the patients will be done by the PI or treating co-investigators. In order to preserve the blind, medication will be administered in identical capsules containing 0 or 200 mg of CBD dissolved in a mixture of self-emulsifying excipients; participants will be delivered multiple 200mg capsules/day for a total of 0 or600 mg CBD/day.

Study medication will be received under a Schedule 1 import license obtained by the PI and will be logged into the approved storage facility upon arrival. Study medication will be re-packaged by unblinded study personnel from the original Tilray bottles into blinded and appropriately labeled bottles for dispensation. The re-bottled, blinded study medication will then be dispensed to participants under the direct supervision of the PI or a designated coinvestigator, as approved by the BNE and DEA. Participants will be required to return all un-used medication, which will be kept securely at the drug storage site until it is sent to a reverse distributor for destruction.

Designated study personnel will keep a log of the study drug accountability and dispensing in accordance with New York State Bureau of Narcotic Enforcement and DEA policies (see below). This process will provide strict safeguarding and accounting of the agent both for internal and external regulatory agencies.

As per Schedule I drug compliance, a biennial inventory shall be prepared and maintained in accordance with New York State and federal statutes. A copy of the inventory will be kept on file with other controlled substance records and shall be kept available for inspection for at least 5 years. The number of study drug-containing capsules will be checked on a weekly basis by two designated study staff members and it will be recorded on a Controlled Substance Accountability Log which includes the following information: 1) date and time of recording, 2) name of controlled substance, 3) amount received (number of capsules), 4) amount dispensed, and 5) amount returned. All other information will be included in the Study Drug Dispensation Log as each individual subject's dose is dispensed. The information included in the Study Drug Dispensation Log is: 1) subject initials/number (plus date of birth as a double identifier), 2) date and time of study drug dispensation, 3) drug name, 4) lot number, and 5) dose. Two designated study team members will sign the Study Drug Dispensation Log. The balance of the remaining medication and any amount returned will be recorded in the Controlled Substance Accountability Log (see above).

## 6.3 Study Behavioral or Social Intervention(s)

All participants will receive Medical Management by a licensed MD or NP, based on the model developed for the NIAAA COMBINE trial [92]. This model provides a low intensity intervention that has some efficacy over no intervention, and is designed to enhance compliance in the context of a clinical trial. Brief counselling sessions provided by a licensed MD or NP focus on: support for recovery, treatment participation, reporting possible adverse effects, and medication compliance. The co-investigator [name] has experience adapting this model in a prior alcohol pharmacotherapy trial [93].

## 6.3.1 Administration of Intervention

CBD (or placebo) will be administered daily for 6 weeks. The first administration of CBD vs. placebo (at T1) will take place at the study site. Participants will remain at the study site with a study team member for approximately 2 hours following the initial administration of each dose of CBD, and participants will not be permitted to leave the study site until they are able to pass a standard field sobriety test (a walk-and-turn task, one-leg stand, Romberg's test, finger-finger test, and counting backwards [85]). If there are no AEs during this time-period or lasting intoxicating effects of the study drug (i.e. participants are able to pass field sobriety tests 2-3 hours after study drug administration), participants will be given a 1- or 2-week supply of the study drug (CBD or placebo) to self-administer daily at home until the next scheduled study visit.

## 6.3.2 Assessment of Subject Compliance with Study Intervention

To maximize medication compliance, we will implement an optional smartphone-assisted medication adherence platform [94] in which the subject takes a video of drug administration at each dose, and transmits this to study personnel. This program has been used successfully in previous studies and includes security provisions that ensure protection of confidentiality and privacy. If the participant is unable to use the smartphone-assisted platform then medication adherence will be ensured using pill counting and meeting with the study nurse practitioner at each visit.

# 7 Study Procedures and Schedule

# 7.1 Study Procedures/Evaluations

## Inclusion/exclusion criteria:

Medical screening by an NP or MD will include medical history and physical exam, liver function tests, complete blood count, urinalysis, menstrual calendar (if female except those menopausal for >1 year since last menstrual period and/or had a bilateral oophorectomy), pregnancy test (if female except those menopausal for >1 year since last menstrual period, had a hysterectomy, and/or had tubal ligation), and vital signs for safety. The licensed provider (NP or MD) will also review participants' controlled substance prescription history using the online Prescription Monitoring Program (PMP) Registry to inform study eligibility. The Structured Clinical Interview for DSM-5 (SCID ) will be used to determine substance use disorder diagnoses and exclusionary psychiatric disorders {First, 1997 #114}. The Life Events Checklist (LEC) and Clinician Administered PTSD Scale (CAPS) for DSM 5 will be used to assess PTSD symptoms [101]. The Concussion Symptom Inventory (CSI) and a modified version of the Ohio State University TBI Identification Method (TBI OHIO) will be used to assess for Traumatic Brain Injury (TBI). The clinical interviews will be conducted by SCID and CAPS trained study clinicians, masters-level study team members and bachelors-level study team members with sufficient psych-assessment training as approved by the study PI. Individuals will have the option to be audiotaped during the screening interview. If the participant consents, audio recordings will be used to ensure quality control and clinical adherence to the protocol. Audio recordings will also be used for voice-marker analysis. If a participant voices that he/she is uncomfortable with the audiotaped interview, he/she can tell a study team member that he/she does not wish to participate in this component of the study. In that case, the participant could still participate in the study but would not complete the audiotaped interview.

PhenX Tier 1 measures and a Locator form will be completed at screening to collect contact information, demographics, BMI, quality of life, HIV risk and status, and substance use measures (age of onset, past 30-day quantity and frequency, lifetime use for alcohol, tobacco, and other substances; www.phenxtoolkit.org). The Clinical Institute Withdrawal Scale- Alcohol, revised (CIWA-Ar) will be used to verify lack of alcohol withdrawal [95], a urine drug screen (UDS) will be done at every in-person study visit (except for visits less than 24 hours from the last visit; i.e. 1 day visit) to verify lack of recent cannabinoid and other drug use, and a urine pregnancy test will be done at each in-person study visit (for women of childbearing potential: if female except those menopausal for >1 year since last menstrual period, had a hysterectomy, and/or had tubal ligation) to verify lack of pregnancy. If subjects are found to have suicidal intentions based on screening tests, appropriate referrals to mental health professionals will be made by the PI.

#### 7.1.1 Confirmation of target CBD plasma levels and measurement of THC levels:

Circulating levels of CBD, THC and THC metabolites (Delta-9 THC, 11-Hydroxy Delta-9 THC and Delta-9 Carboxy THC) will be obtained from CBD-treated participants baseline (pre-CBD levels), following 45 minutes (T1- 45min post-CBD levels), 1 day (T2- 45min post-CBD levels), 1 week (T3- 45min post-CBD and pre-CBD levels), 2 weeks (T4- 45min post-CBD and pre-CBD levels), 4 weeks (T6- 45min post-CBD and pre-CBD levels), 6 weeks (T8- 45min post-CBD and pre-CBD levels), and 7 weeks (T9- pre-CBD levels) after the first CBD vs. placebo dose. All of these levels (CBD, THC and THC metabolites) will be determined via High Performance Liquid Chromatography/Tandem Mass Spectrometry (LC-MS/MS) at [name] Lab at the Department of Cell Biology at NYU Langone Health.

#### 7.1.2 Measurement of plasma Anandamide levels:

Plasma AEA levels will be obtained at baseline (pre-CBD levels), following 45 minutes (T1- 45min post-CBD levels), 1 day (T2- 45min post-CBD levels), 1 week (T3- 45min post-CBD and pre-CBD levels), 2 weeks (T4- 45min post-CBD and pre-CBD levels), 4 weeks (T6- 45min post-CBD and pre-CBD levels), 6 weeks (T8- 45min post-CBD and pre-CBD levels), and 7 weeks (T9- pre-CBD levels) after the first CBD vs. placebo dose. Plasma AEA levels will be determined via High Performance Liquid Chromatography/Tandem Mass Spectrometry (LC-MS/MS)at [name] Lab at the Department of Cell Biology at NYU Langone Health .

#### 7.1.3 Safety:

#### #S17-00949

Safety will be assessed by collection of adverse events using the Systemic Assessment for Treatment of Emergent Events (SAFTEE) [103] measure at all visits after treatment is initiated. LFTs will be obtained at screening, as well as weeks 2, 6 and 7 to assess the liver function during and after treatment with study medication. Risk of suicidality will be assessed by a licensed MD, NP, Psychologist, or C-SSRS certified study team member using the Columbia-Suicide Severity Rating Scale (C-SSRS) [98] as part of each study visit, including screening and baseline. If the patient endorses significant suicidality/homicidality, a safety assessment will be conducted, referrals provided, and if indicated, a case report form will be written if indicated, a follow-up phone call within 48 business hours of providing referrals will be completed. If and when appropriate, the clinicians will then contact the overall study PI ([name]) for further consultation. The appropriate procedures for all study team members to follow in the case of a psychiatric or medical emergency are outlined in detail in the Medical and Psychiatric Emergencies SOP.

### 7.1.4 **Psychomotor and subjective effects of CBD:**

Basic motoric and cognitive function will be evaluated throughout treatment with several established field sobriety tests, including a walk-and-turn task, one-leg stand, Romberg's test, finger-finger test, and counting backwards [85]. The Addiction Resource Center Inventory (ARCI), 49-item version [86], will be used as a measure of the intoxicating effects and abuse potential of CBD. Breath Alcohol Concentration (BAC) will also be measured to ensure participants are not under the influence of alcohol during administration of these tasks.

## 7.1.5 **Cognitive Function:**

Several established neuropsychiatric and cognitive tasks will be administered to evaluate the impact of CBD vs. placebo treatment on cognitive domains potentially affected by CBD and/or THC. The Rey Auditory Verbal Learning Task (RAVLT) will be used to assess episodic memory [87], the Mental Rotation Task (MRT) will evaluate visuospatial ability [88] [89], a Time Reproduction Task (TRT) will measure encoding and retrieval of time intervals [67] and several WM Span tasks (OSpan, RSpan, SymSpan, RotSpan) will measure working memory capacity [90, 91]. Cognitive function will be assessed one day after CBD or placebo treatment and at 6 weeks following treatment.

### 7.1.6 AUD-related measures:

The Penn Alcohol Craving Scale (PACS) [79] will be used to assess craving. This scale has 5 Likert-scaled items with excellent internal consistency and evidence of predictive, construct, and discriminant validity. Craving will be assessed before CBD or placebo treatment (baseline), at weeks 1, 4 and 6 of treatment, and one week after the completion of treatment (week 7). Mood and Anxiety will be measured with the Beck Anxiety Inventory (BAI) [99] and Beck Depression Inventory-II (BDI-II) [100] scales before CBD or placebo treatment (baseline), at weeks 1, 4 and 6 of treatment, and one week after the completion of treatment, and one week after the completion of treatment (baseline), at weeks 1, 4 and 6 of treatment, and one week after the completion of treatment (week 7). Self-efficacy will be assessed using the Alcohol Abstinence Self-Efficacy Scale (AASE) [81], a self-report questionnaire which has been used widely in the alcohol treatment research, both as a predictor of outcome and as a patient-treatment matching variable [82]. Self-efficacy will be assessed before CBD or placebo treatment (week 7).

#### 7.1.7 **PTSD-related measures:**

PTSD symptoms will be assessed with the PTSD checklist for the DSM-5 (PCL-5) [96]. Baseline PTSD symptoms will be defined as the total PCL-5 score at baseline. The primary PTSD outcome is the total score of the PCL-5 for each week administered. PTSD symptoms will be assessed before CBD or placebo treatment (baseline), at weeks 2, 4 and 6 of treatment, and one week after the completion of treatment (week 7).

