The proposed study is a double-blind, randomized proof-of-concept study designed to assess feasibility and contrast effects of CBD treatment to those of placebo on safety, drinking-related outcomes and PTSD/subthreshold PTSD related outcomes in patients with AUD+PTSD/subthreshold PTSD. We will evaluate the safety of an extended daily CBD treatment regimen in an AUD+PTSD/subthreshold PTSD population and measure resulting CBD, THC, and anandamide levels. We will also generate preliminary data on the impact of CBD on alcohol use, PTSD symptoms, a human laboratory traumatic stress induced craving task, neuropsychological and neurophysiological domains implicated in AUD and PTSD/subthreshold PTSD, and cognitive ability. Cannabidiol levels will be obtained from CBD-treated participants to estimate the plasma levels corresponding with putative therapeutic effects and to determine whether dose accumulation occurs. THC levels will be obtained from CBD-treated participants to determine whether CBD metabolites are converted into THC, as has been suggested in the literature [77]. Anandamide levels will be obtained from all participants to test whether CBD elevates plasma anandamide, and to provide preliminary data for relating anandamide levels to putative therapeutic effects. Following screening and baseline assessments, 48 participants will be randomized in a 5:3 ratio to receive either 600mg CBD/day (PO) or placebo respectively for 6 weeks (N=30 participants on CBD and N=18 participants on placebo). Safety measures (adverse events, cognitive and motoric function), drinking related outcomes and PTSD symptoms will be assessed weekly throughout the study. Human laboratory tasks, neuropsychological domains implicated in AUD and PTSD/subthreshold PTSD and cognition will be assessed at baseline and at the end of treatment. Measurement of circulating levels of Delta-9 THC, 11-Hydroxy Delta-9 THC and Delta-9 Carboxy THC will be obtained from CBD-treated participants only at baseline, 45 minutes, 1 day, 1 week, 2 weeks, 4 weeks, 6 weeks, and 7 weeks after treatment with the first dose of CBD vs. placebo. Anandamide levels will be obtained from both CBD- and placebo-treated participants at the aforementioned timepoints.

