## 3.2 Secondary Objectives

Secondary objectives of this study are as follows.

- To assess the effect of CBD upon plasma CBD and THC levels when administered to patients with AUD+PTSD/subthreshold PTSD. We predict that within-group plasma CBD levels will stabilize within one week, i.e. 45 minutes post-CBD dosing levels obtained after 1 week of treatment will not differ from those obtained after 4 weeks of treatment.
- 2) To contrast the effects of CBD to those of placebo on psychological and cognitive domains relevant to AUD and PTSD/subthreshold PTSD. Relative to placebo, we predict that CBD will improve self-report measures of craving, anxiety, mood, and self-efficacy, and improve cognitive function. We will also specifically target the domain of traumatic stress induced craving using a human laboratory task. We predict that relative to placebo, CBD will lead to a greater attenuation in subjective traumatic stress and alcohol cue-induced craving and accompanying physiological stress response.
- 3) To assess the effect of CBD on plasma anandamide levels. We will contrast levels of plasma anandamide between samples taken at baseline and after CBD treatment, and between samples taken at predicted preand 45 minutes post-dosing CBD levels. We predict that relative to placebo, CBD will lead to an increase in plasma anandamide between these time points.
- 4) To assess the temporal relationship between the onset in reduction of PTSD symptoms and the onset in reduction of AUD symptoms. We predict that a reduction in PTSD symptoms will precede a reduction in

Exploratory Aim 1: To examine voicemarkers as a function of a patient's AUD and PTSD status and to develop assessment models that use lexical and prosodic features to classify a patient's AUD and PTSD status.

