# 4 Study Design and Endpoints

# 4.1 Description of Study Design

The proposed study is a phase I/II, single-center, double-blind, randomized proof-of-concept study designed to assess safety and feasibility in the AUD+PTSD/subthreshold PTSD population and contrast effects of CBD treatment to those of placebo on drinking-related outcomes and PTSD symptoms. We will evaluate the safety of an extended daily CBD treatment regimen in an AUD+PTSD/subthreshold PTSD population, measure resulting plasma and CBD and THC levels, generate preliminary data on the impact of CBD on alcohol consumption and PTSD symptoms, assess the effect of CBD on a human laboratory measure of traumatic-stress induced craving and neuropsychological measures relevant to AUD and PTSD/subthreshold PTSD, and assess the effect of CBD dosing no plasma anandamide levels.

150 participants are expected to be enrolled in the study prior to screening and randomization. Following screening and baseline assessments, 48 participants who fully meet study criteria are expected to be randomized in a 5:3 ratio to receive either 600mg CBD/day (PO) or placebo respectively for 6 weeks (N=30 participants on CBD and N=18 participants on placebo). This dose was selected to optimize anxiolytic affects to target stress induced alcohol craving. Assessments of drinking and PTSD related outcomes will be completed at baseline and weekly over 6 weeks of treatment, with an assessment one week following the end of treatment. The human laboratory task and assessments of cognitive function will be completed at baseline and at the end of 6 weeks of treatment. Measurement of circulating levels of CBD, THC, and THC metabolites (Delta-9 THC, 11-Hydroxy Delta-9 THC and Delta-9 Carboxy THC) will be obtained from CBD-treated participants at baseline, 45 minutes, 1 day, 1 week, 2 weeks, 4 weeks, 6 weeks, and 7 weeks after treatment with the first dose of CBD vs. placebo. Anandamide levels will be obtained from both CBD- and placebo-treated participants at the aforementioned time-points.

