# 4.2 Study Endpoints

# 4.2.1 Primary Study Endpoints

The primary study endpoint for alcohol use will be number of drinks per day assessed by the Time Line Follow Back methodology [78]. The primary study endpoint for PTSD symptoms will be the PCL-5 total score. Safety will be assessed by collection of adverse events at all visits after treatment is initiated in addition to LFTs collected at screening, as well as weeks 2, 6, and 7 to assess the liver function during and after treatment

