#### **PTSD-related measures**

The PCL-5 will be administered at baseline, weeks 2, 4, 6 and 7. In addition to the PCL-5 score (primary PTSD endpoint), childhood trauma (child abuse and neglect) will be assessed at baseline using the self-report Childhood Trauma Questionnaire (CTQ) (28 item).

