## 1 week (T3)

#### +/- 5 days

- Perform alcohol breathalyzer to obtain BAC
- Collect urine for urine drug analysis and urine pregnancy test (if applicable)
- Collect blood and plasma for CBD, Delta-9 THC, 11-Hydroxy Delta-9 THC, Delta-9 Carboxy THC and Anandamide levels (post- and pre-CBD dosing levels)
- Record adverse events as reported by participant or observed by investigator
- Record vital signs, concurrent medications, menstrual calendar (if applicable), and results of evaluations of safety, psychomotor/subjective effects
- Evaluate and record AUD related measures
- Evaluate and record alcohol use
- Provide participants with sufficient study medication to administer daily until the next scheduled visit (1 week), and instructions for how to use the study medication and document their use
- Record participant's adherence to treatment program
- Administer medical management session

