### 20.3.10 Exploratory Analyses

### For Exploratory Hypothesis 1, relationship between PTSD/subthreshold PTSD and AUD symptom change

Symptom onset is defined to be the first week in which the patient has 50% reduction in the number of drinks per day for the primary alcohol outcome and a 30% reduction in the Total Score of the PCL-5 that is sustained for at least two weeks. Onset of a positive clinical outcome will be described by a "cure model." The form of a cure model is H(t) = 1 - p + pS(t); where H(t) is the probability of onset at a time greater than t, p represents the probability of success and S(t) is the distribution of time to success, conditional on success occurring. The parameters will be estimated based both on Kaplan Meier methods and parametrically. The equality of the values of p for the two treatment arms will be tested using a nonparametric likelihood ratio test. For the parametric test, a logistic will be used to model p and a Weibull survival distribution will be used to model time to failure, S(t). Both allow the use of covariates. The comparison will be based on a likelihood ratio test and the median time to onset of S(t).

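### PCL-5 timing is stated two ways; on the detailed schedule, PTSD onset is dated in two-week steps and drinking onset in one-week steps, an artificial PTSD lag of about half a week

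*Combined protocol and SAP*

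**What the plan says.** Section 3.2 lists as secondary objective 4: "To assess the temporal relationship between the onset in reduction of PTSD symptoms and the onset in reduction of AUD symptoms". It predicts that PTSD improves first. Section 20.2 repeats the prediction but labels it Exploratory Hypothesis 1.

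The timing of PTSD assessment is stated in two ways.

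- Weekly: section 4.1 says "Assessments of drinking and PTSD related outcomes will be completed at baseline and weekly over 6 weeks of treatment", and section 2.3 says "drinking related outcomes and PTSD symptoms will be assessed weekly throughout the study".
- Weeks 2, 4, 6 and 7 only: section 4.2.2 (PTSD-related measures) says "The PCL-5 will be administered at baseline, weeks 2, 4, 6 and 7", and section 7.1.7 says "PTSD symptoms will be assessed before CBD or placebo treatment (baseline), at weeks 2, 4 and 6 of treatment" and then adds week 7. The visit lists in section 7.3.3 agree with this second version. PTSD measures appear at T4, T6, T8 and T9. The week-1 visit (T3) lists only "Evaluate and record AUD related measures", and the week-3 and week-5 calls (T5, T7) list neither PTSD measures nor alcohol use.

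Section 4.2.1 defines the drinking endpoint as "number of drinks per day assessed by the Time Line Follow Back methodology", and section 4.2.2 summarises several drinking measures per treatment week.

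Section 20.3.10 dates onset to the first week with a 50% reduction in drinks per day and "a 30% reduction in the Total Score of the PCL-5 that is sustained for at least two weeks". It fits cure models by Kaplan-Meier and Weibull methods. It does not mention unequal assessment grids or interval censoring.

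**The concern.** An onset can be recorded only when the outcome is observed. If the PCL-5 is seen every second week and drinking every week, a PTSD improvement in an odd week is dated one week late, while a drinking improvement in that week is dated correctly. The trial's question is which comes first, over six weeks of treatment, so a one-week dating error is large relative to the quantity of interest.

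At stake is the interpretation of one sequence analysis. A result showing no PTSD lead, or drinking first, could not be told apart from an effect of the visit schedule. The primary efficacy contrasts and the safety conclusions are not affected.

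**Working it through.** The plan gives no figure on this point to reproduce; its only power figure concerns a t test of means.

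**Inputs.** PCL-5 at weeks 2, 4, 6 and 7 (4.2.2, 7.1.7, visit lists). Drinking resolved to single weeks 1, 2, 3 and so on (4.2.1, 4.2.2). Onset is the first recorded week meeting the threshold (20.3.10).

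**Assumptions.** Visits fall on nominal days. Each outcome makes a lasting step change in its true onset week. The Time Line Follow Back covers every day between visits; its on-treatment window is not stated.

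**Average delay.** If true onset is uniform over an interval of width h, rounding up adds h/2 on average. PCL-5: 2/2 = 1.0 week. Drinking: 1/2 = 0.5 week. Net artificial PTSD lag: 1.0 - 0.5 = 0.5 week.

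**Same-week onset.**

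| True week (both) | 1 | 2 | 3 | 4 | 5 | 6 |
|---|---|---|---|---|---|---|
| Recorded PTSD | 2 | 2 | 4 | 4 | 6 | 6 |
| Recorded drinking | 1 | 2 | 3 | 4 | 5 | 6 |
| Scored first | drinking | tie | drinking | tie | drinking | tie |

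Drinking first 3/6 = 50%, tie 50%, PTSD first 0%. For weeks 1-4 alone the split is 2/4, 2/4 and 0.

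**PTSD truly one week earlier** (PTSD weeks 1-5, drinking weeks 2-6): tie, PTSD, tie, PTSD, tie. Ties are 3/5 = 60%; for PTSD weeks 1-4 they are 2/4.

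**PTSD truly two weeks earlier** (four cases): all are scored PTSD first, with the mean lead reduced from 2 to 1.5 weeks.

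**Drinking truly one week earlier** (five cases): all are scored drinking first. The mean recorded lead is (1+2+1+2+1)/5 = 1.4 weeks, against a true 1.

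**Independent onsets, each uniform on weeks 1-6** (36 pairs).

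| Grid | PTSD first | Tie | Drinking first |
|---|---|---|---|
| Both weekly | 15/36 = 41.7% | 6/36 = 16.7% | 15/36 = 41.7% |
| Detailed schedule | 12/36 = 33.3% | 6/36 = 16.7% | 18/36 = 50.0% |
| Both on the PCL-5 grid | 12/36 = 33.3% | 12/36 = 33.3% | 12/36 = 33.3% |

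**Sensitivity to the onset distribution.** Exponential onset times were simulated with assumed medians of 1.5, 2.5 and 4 weeks, the same for both outcomes, keeping pairs with both onsets by week 6. PTSD was recorded first in 25.6%, 30.0% and 32.0% of pairs, against about 50% in truth. Drinking was recorded first in 55.5%, 53.0% and 51.6%. The mean artificial lag was 0.61, 0.58 and 0.55 week.

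**The two-week rule.** Week 2 can be confirmed at week 4 (4 - 2 = 2) and week 4 at week 6 (6 - 4 = 2). Week 6 is followed only by week 7 (7 - 6 = 1). On nominal days, PCL-5 onset can therefore be confirmed only at week 2 or week 4.

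**A repair that fails.** Suppose drinking is averaged over weeks 1-2, 3-4 and 5-6 to match the PCL-5 visits. If drinking falls by a fraction r from week 2 onward, the week 1-2 average falls by only (0 + r)/2 = r/2, which misses the 50% threshold unless r = 100%. Drinking onset then moves to the next block. For r between 50% and 100%, same-week onsets at weeks 1-4 score tie, PTSD, tie, PTSD. The artefact is reversed, not removed.

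**The case against.** The strongest objection is that no planned test of order exists to be biased. The one contrast that section 20.3.10 names explicitly is between the two arms. Both arms share the same PCL-5 schedule, so that contrast does not acquire this ordering artefact. The sentence defining onset can even be read as one composite event that needs both reductions, and it is unclear whether the sustained requirement covers drinking. This stands: the artefact belongs to any plain comparison of recorded onset weeks that is later written for the objective.

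Three stronger readings are tempting, and the documents do not support them.

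- A reader might infer that the overall error runs against the trial's prediction. Only the grid component has that direction. Drinking must fall by 50% and the PCL-5 by 30%; the stricter drinking threshold could delay drinking onset, so the net direction is unknown.
- A reader might infer that late PTSD responders are lost. In a Kaplan-Meier or cure model, an unconfirmed week-6 response would normally be censored. The windows of +/- 5 days also allow T8 and T9 to be as far apart as 7 + 5 + 5 = 17 days.
- A reader might infer a further delay from past-month PCL-5 recall. Section 7.3.6 names that period only for the clinical re-screen; no on-treatment recall period is stated.

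It is also fair to say that an interval-censored analysis would handle unequal grids, but none is planned. If the weekly statements in 2.3 and 4.1 govern, the grid problem disappears; the detailed sections and every visit list say otherwise.

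**Conclusion.** The point holds in two parts. First, the documents contradict themselves on when a primary PTSD measure is collected, and this needs reconciling in any case. Second, under the detailed schedule, a plain comparison of recorded onset weeks carries an artificial PTSD lag of about 0.5 week (0.55 to 0.61 under the exponential assumptions). Same-week onsets are never scored as PTSD first, and about half of true one-week PTSD leads become ties, while two-week leads keep their order.

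The size rests on nominal visit days, step changes, the assumed onset distributions and week-level drinking data. The importance is moderate: the hypothesis is secondary in 3.2 but exploratory in 20.2 and 20.3.10, in a 48-participant pilot. It is worth fixing because the comparison itself is still to be written and section 20.1 leaves the formal SAP open until before database lock and unblinding.

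**What to change.** Reconcile sections 2.3 and 4.1 with 4.2.2, 7.1.7 and the visit lists. Then take one of two routes.

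(a) Give the self-report PCL-5 at the existing week 1, 3 and 5 contacts (T3, T5, T7), as 2.3 and 4.1 already state, with one fixed recall period throughout treatment. Cost: one short questionnaire at three existing contacts, two of which are phone calls.

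(b) If visits cannot change, amend 20.3.10 so that drinking onset is evaluated at the PCL-5 time points, using drinks per day in the single week ending at T4, T6 and T8, not two-week averages. Alternatively, keep both grids and use an interval-censored analysis. Cost: SAP wording only. Drinking onset on the common grid is coarser, and one-week resolution is not recovered: a true one-week PTSD lead is still a tie in 60% of cases, although same-week onsets now always tie.

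Under either route, state that PTSD and drinking onsets are separate events, write down the comparison between them, and apply the same sustained rule to both, for example met at two consecutive assessments with T9 confirming T8. State how unconfirmed responses are censored, and that the 30% and 50% thresholds also influence the recorded order.
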